3.2 Post Study Access to Therapy

At the end of the treatment period, the sponsor will not continue to supply study drug to subjects/investigators unless the sponsor chooses to extend the study. If the investigator considers that the subject should receive continuous VTE prevention after the Day 29 visit, the investigator should ensure that the subject receives appropriate standard of care to provide VTE prevention.

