3.4.1 Prohibited and/or Restricted Treatments

- 1) Concurrent prophylactic or therapeutic treatment with LMWH, unfractionated heparin, other oral anticoagulant, or systemic tPA (heparin flushes to maintain CVAD patency and local tPA to restore CVAD patency are permitted)
- 2) Any anti-platelet therapy with aspirin or thienopyridines such as clopidogrel, ticagrelor, or prasugrel.
- 3) Concomitant systemic treatment with strong inhibitors of both cytochrome P450 3A4 (CYP3A4) and P-glycoprotein (P-gp), such as ketoconazole, itraconazole, posaconazole, telithromycin, clarithromycin, indinavir, nelfinavir, saquinavir, cobicistat, and ritonavir.
- 4) Concomitant systemic treatment with strong inducers of both cytochrome P450 3A4 (CYP3A4) and P-glycoprotein (P-gp), such as rifampin, carbamazepine, phenytoin and St. John's Wort.

- 5) Chronic daily use of nonsteroidal anti-inflammatory drugs (NSAIDs, eg, naproxen, ibuprofen, diclofenac) may increase the risk of bleeding. Therefore, concomitant use of NSAIDs more than 7 days is prohibited.

During the entire study period, no other investigational agents, other than apixaban should be administered to the patient.

Note: Fluconazole, topical azole antifungal agents, trimethoprim-sulfamethoxazole, H2-antagonists and proton pump inhibitors are permitted.

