8.2 Populations for Analyses

- The Randomized/Intent-To-Treat (ITT) population consists of all subjects who were randomized to a treatment, regardless of whether they received study drug or not. Except as noted otherwise, Randomized/ITT Population will be used for the evaluation of efficacy.
- The Modified Intent-To-Treat (mITT) population includes randomized subjects who have either an adjudicated event making up the primary efficacy endpoint or evaluable end of study imaging evaluations, including ultrasound and echocardiogram.
- The Evaluable population will include the Randomized/ITT population except those subjects with relevant protocol deviations expected to affect the primary efficacy endpoint.
- The safety population includes all randomized subjects since there is no intervention on top of standard care in the control arm and will be used for the evaluation of safety.
- The analysis population for pharmacokinetic assessments will include subjects who have received at least one dose of apixaban and have a pharmacokinetic sample collected.
- The analysis population for anti-FXa assessments will include subjects who have received at least one dose of apixaban and have anti-FXa samples collected.

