6 STUDY PERIODS, TREATMENT REGIMENS AND POPULATIONS FOR ANALYSES

6.1 Study Periods

The term “**Intended Treatment Period**” will refer to the period from day of randomization through Day 29 visit. This period will be the basis for the summaries of efficacy.

The term “**Treatment Period**” will refer to the period from the day of randomization through the end of treatment Day 29 visit or early discontinuation from study (whichever comes first).

The term “**On-treatment Period**” will refer to the period from the day of first dose through the last dose of study medication. This period will be the basis for the summaries of apixaban safety only, because only the apixaban arm will have dose information.

The term “**Follow-up Period**” will refer to the period starting the day after the Day 29 visit or early discontinuation to Day 35 days visit.

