6.3 Populations for Analyses

The following population will be used for the analyses.

Enrolled Population

The Enrolled Subjects population consists of all subjects who signed informed consent.

Randomized /Intent-To-Treat (ITT) Population

The Randomized/Intent-to-treat (ITT) population consists of all subjects who were randomized to a treatment, regardless of whether they received study drug or not. Except as noted otherwise, the ITT Population will be used for evaluation of efficacy.

Modified Intent-To-Treat (mITT) Population

The mITT population includes randomized subjects who have either an adjudicated event making up the primary efficacy endpoint or evaluable end of study imaging evaluations, including ultrasound and echocardiogram

Evaluable Population

The Evaluable population will include the Randomized/ITT population, except those subjects with relevant protocol deviations expected to affect the primary efficacy endpoint.

The relevant protocol deviations, used to determine exclusions, are listed in [Section 7.2](#).

Safety Population

The safety population for safety endpoints includes all randomized subjects, since there is no intervention on top of standard of care in the control arm. Additional analyses will be performed for subjects treated with apixaban.

Pharmacokinetic (PK) Population

The analysis population for pharmacokinetic assessments will include subjects who have received at least one dose of apixaban and have a pharmacokinetic sample collected.

Pharmacodynamics (PD) Population

The analysis population for anti-FXa assessments will include subjects who have received at least one dose of apixaban and have anti-FXa samples collected.

Subgroup Populations

Table 6.3-1 shows the subpopulations of interest for analyses of efficacy and bleeding.

Table 6.3-1: Subgroups of Interest for Efficacy and Bleeding Assessments

Grouping Variable	Subgroups
Geographic region	North America Europe Latin America Asia/Pacific
Age (stratification variable)	< 10 years old ≥10 to < 18 years old
Age category	Young Children 1 year to <2 years Young Children 2 years to 6 years Children 6 years to <12 years Adolescents 12 years to <18 years
Ethnicity	Hispanic/Latino

Table 6.3-1: Subgroups of Interest for Efficacy and Bleeding Assessments

Grouping Variable	Subgroups
	Not Hispanic/Latino
Gender	Male Female
Race	White Black / African American Asian Other
Weight	< 35 kg ≥35 kg

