7.2 Study Conduct

7.2.1 Protocol Deviations

Subjects who deviate from protocol conditions (e.g., important inclusion/exclusion criteria) will be reported as having important protocol deviations. Important protocol deviations that are determined to affect the primary efficacy results are deemed Relevant Protocol Deviations. Relevant protocol deviations will be identified for all subjects who are randomized. Relevant Protocol Deviation Criteria are as follows:

- Subject randomized to apixaban group but not dosed with apixaban for > 3 consecutive days (excluding protocol defined interruptions)
- Error in treatment assignment resulting in a subject being dosed with an incorrect treatment for > 3 consecutive days
- Randomized subjects without a functioning CVAD placed between Day -7 and Day 4 \pm 3 of induction chemotherapy
- Randomized subjects with a prior history of documented DVT or PE in the past 3 months
- Randomized subjects with known inherited bleeding disorder or coagulopathy
- Prohibited and/or Restricted Treatments during study period
 - Any anti-platelet therapy with aspirin or thienopyridines such as clopidogrel, ticagrelor, or prasugrel.
 - Concomitant systemic treatment with strong inhibitors of both cytochrome P450 3A4(CYP3A4) and P-glycoprotein (P-gp), such as ketoconazole, itraconazole, posaconazole, telithromycin, clarithromycin, indinavir, nelfinavir, saquinavir, cobicistat, and ritonavir.
 - Concomitant systemic treatment with strong inducers of both cytochrome P450 3A4 (CYP3A4) and P-glycoprotein (P-gp), such as rifampin, carbamazepine, phenytoin and St. John's Wort.
 - Chronic daily use of nonsteroidal anti-inflammatory drugs (NSAIDs, eg, naproxen, ibuprofen, diclofenac) may increase the risk of bleeding. Therefore, concomitant use of NSAIDS more than 7 consecutive days is prohibited.

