7.5.1 Primary Efficacy Analysis

The primary objective is compare the effect of prophylactic oral or enteric apixaban versus no administration of systemic prophylactic anticoagulant during induction chemotherapy, on the composite endpoint of adjudicated non-fatal asymptomatic and symptomatic DVT, pulmonary embolism (PE), and CVST; and VTE-related-death during intended treatment period.

To conclude superiority of apixaban versus standard care on the primary efficacy endpoint during intended treatment period, the upper bound of the two-sided 95% CI for the relative risk (p_a/p_e) must be less than 1. This condition corresponds to a test of hypothesis $H_0: p_a = p_e$ against the alternative $H_a: p_a < p_e$ using the Mantel-Haenszel test stratified by age group (<10 years or ≥ 10 to <18 years) performed at the one-sided $\alpha = 0.025$ level. Here p_a and p_e represent the proportions of subjects with primary efficacy endpoints in the apixaban and standard care groups, respectively.

Two-sided 95% CI for the relative risk (p_a/p_e) will be reported for the primary efficacy endpoint. The p-value associated with the superiority test will also be reported.

The primary efficacy analyses will be performed based on the randomized/ITT population. Subjects with no symptomatic event and no ultrasound or echocardiogram assessment will be counted as not having an event.

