7.5.1.1 Sensitivity Analyses for Primary Efficacy Endpoint

In order to assess the robustness of the effectiveness of apixaban relative to standard care, the following sensitivity analyses will be performed for the primary efficacy endpoint:

[figure not shown]
- An analysis will be performed using the mITT Population.

- An analysis will be performed for all randomized subjects with missing primary endpoint or non-evaluable imaging data to be assessed via multiple imputation using 1000 repetitions, with imputation of events for patients with missing data in both treatment groups based on the event rate observed from the corresponding stratum in the standard-of-care arm
- If results from the primary efficacy analysis show a significant difference between treatment groups, then a “tipping point” analysis will be performed with a non-stratified analysis. In each analysis, subjects with missing data in the standard-of-care arm will be assumed to be event-free, while progressively more subjects with missing data in the apixaban arm will be assigned with an event, up to the limit of the number of subjects with missing data in the apixaban arm. The number of subjects in the apixaban arm imputed with event that would change the result from significant to non-significant would be noted.
- An analysis will be performed based on the Evaluable Population, if at least 10% of subjects have a relevant protocol deviation.

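### The SAP's list of relevant deviations omits systemic anticoagulants, so a control child anticoagulated before any event stays in the Evaluable population and outside its 10% trigger

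*SAP*

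**What the plan says.** Protocol 3.4.1 numbers five prohibited treatments. Item 1 is "Concurrent prophylactic or therapeutic treatment with LMWH, unfractionated heparin, other oral anticoagulant, or systemic tPA"; flushes and local tPA to keep or restore line patency are exempt. Items 2 to 5 are antiplatelet drugs, strong dual CYP3A4/P-gp inhibitors, strong dual inducers, and NSAIDs for more than 7 days.

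Protocol 8.2 defines the Evaluable population as all randomized subjects "except those subjects with relevant protocol deviations expected to affect the primary efficacy endpoint". SAP 6.3 makes this operational: "The relevant protocol deviations, used to determine exclusions, are listed in" Section 7.2. SAP 7.2.1 then gives the criteria as a complete list, with no wording to mark them as examples. Its sub-list headed "Prohibited and/or Restricted Treatments during study period" holds items 2 to 5 almost unchanged (the NSAID item now requires consecutive days). Item 1 is not there.

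SAP 7.5.1.1 uses the list twice, to decide who is excluded and to decide whether the analysis runs: "An analysis will be performed based on the Evaluable Population, if at least 10% of subjects have a relevant protocol deviation". The primary analysis does not use it: "The primary efficacy analyses will be performed based on the randomized/ITT population".

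**The concern.** The endpoint is VTE and the control condition is no systemic anticoagulant. Of the five prohibited treatments, a systemic anticoagulant given to a control child is the one most directly expected to affect that endpoint, so it meets the Protocol 8.2 test more clearly than the four that were listed.

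The list as written gives odd results:

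- A control child on NSAIDs for more than 7 consecutive days is excluded. A control child on prophylactic LMWH is not.
- A control child on itraconazole is excluded, although that child takes no apixaban for it to interact with.
- An apixaban child left undosed for more than 3 consecutive days (outside protocol-defined interruptions) is excluded. The mirror-image departure, a control child who is anticoagulated, is not.

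At stake are the membership of the Evaluable population and the count that triggers its analysis. The trial is open-label, so clinicians know which children are unprotected, and contamination of the control arm is a departure a reader would expect this analysis to address.

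**Working it through.** **1. Item-by-item comparison**

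| Protocol 3.4.1 | In SAP 7.2.1? |
|---|---|
| 1. LMWH, unfractionated heparin, other oral anticoagulant, systemic tPA | No |
| 2. Antiplatelet therapy | Yes |
| 3. Strong dual CYP3A4/P-gp inhibitors | Yes |
| 4. Strong dual CYP3A4/P-gp inducers | Yes |
| 5. NSAIDs beyond 7 days | Yes |

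The other SAP criteria cover missed apixaban, an error in treatment assignment, the CVAD, prior DVT or PE, and bleeding disorder or coagulopathy. The nearest, wrong treatment for more than 3 consecutive days, requires an assignment error. It does not reach a correctly assigned control child given LMWH by clinical choice.

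**2. The plan's own figures** (SAP 5: about 500 subjects, 1:1, one-sided 0.025, Pearson chi-square)

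Power = Φ{[Δ − 1.96·√(2p̄(1−p̄)/n)] / √([p₁(1−p₁) + p₂(1−p₂)]/n)}.

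- 17% v 8.5%, n = 250 per arm: (0.085 − 0.0585)/0.0296 = 0.897, power 81.5%.
- 20% v 10%, n = 200 per arm after 20% exclusion: (0.100 − 0.0700)/0.0354 = 0.849, power 80.2%.

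Both agree with the stated value of more than 80%. The omission does not touch them. The 17% and 8.5% rates are used below.

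**3. Effect on the trigger**

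The trigger is 0.10 × 500 = 50 subjects. Assume 2%, 10% or 20% of 250 controls are anticoagulated before any event and have no other listed deviation, which is 5, 25 or 50 children. With item 1 listed, the analysis needs 50 − 5 = 45, 50 − 25 = 25, or 50 − 50 = 0 other deviators. As written it needs 50. At 2%, the omission decides whether the analysis runs only when there are 45 to 49 other deviators.

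**4. Effect on the relative risk**

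Let c be the contaminated share of controls, k the untreated risk of those children relative to other controls, and e the proportional risk reduction from the anticoagulant. The overall untreated control rate is fixed at 17% and apixaban at 8.5%, so the true RR is 0.50.

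- Untreated rate in the other controls: r = 0.17/(1 − c + ck)
- Control rate if contaminated children are kept: (1 − c)r + ck·r(1 − e)
- Control rate if they are removed: r
- RR = 0.085/rate

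Example (c = 0.10, k = 3, e = 0.5): r = 0.17/1.20 = 14.17%. Kept: 0.90r + 0.15r = 1.05r = 14.88%. RR is 0.571 kept and 0.600 removed.

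| c | k | e | Kept rate | RR kept | Removed rate | RR removed |
|---|---|---|---|---|---|---|
| 2% | 1 | 0.50 | 16.83% | 0.505 | 17.00% | 0.500 |
| 5% | 1 | 0.50 | 16.58% | 0.513 | 17.00% | 0.500 |
| 10% | 1 | 0.50 | 16.15% | 0.526 | 17.00% | 0.500 |
| 20% | 1 | 0.50 | 15.30% | 0.556 | 17.00% | 0.500 |
| 10% | 2 | 0.25 | 16.23% | 0.524 | 15.45% | 0.550 |
| 10% | 2 | 0.50 | 15.45% | 0.550 | 15.45% | 0.550 |
| 10% | 2 | 0.75 | 14.68% | 0.579 | 15.45% | 0.550 |
| 10% | 3 | 0.50 | 14.88% | 0.571 | 14.17% | 0.600 |
| 2% | 3 | 0.50 | 16.51% | 0.515 | 16.35% | 0.520 |
| 5% | 3 | 0.50 | 15.84% | 0.537 | 15.45% | 0.550 |

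The kept rate is r[1 + c(k(1 − e) − 1)]. For k of 1 or more, removal therefore brings the RR nearer 0.50 only when k(1 − e) is below 1. At c = 2%, with k from 1 to 3 and e from 0.25 to 0.75, kept values run from 0.503 to 0.523 and removed values from 0.500 to 0.520.

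**The case against.** The strongest objection is that little depends on this. The ITT analysis, the mITT analysis, the multiple imputation and the tipping-point analysis do not use the list. The one analysis that does may never run, and at low contamination the RR barely moves. Keeping treated controls pulls the RR toward 1, so the omission does not favour apixaban. If clinicians chose higher-risk controls, removal can make the estimate worse. All of this stands and limits the size of the finding. It does not justify a list that fails its own definition.

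The omission may also be deliberate. Protocol 3.5 leaves management of events to local practice and allows anti-thrombotic therapy when study drug is stopped for a suspected event, so a blanket rule could remove endpoint cases. That is a reason for a time limit. The SAP gives no reason at all.

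A third objection is that these children are reported anyway, as important deviations (SAP 7.2.1) and in the medication table (SAP 7.4.2). That is true, but neither text separates use before an event from treatment of one, and neither changes who is in the Evaluable population.

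The fix can itself be criticised. It sets no minimum duration, but the listed antiplatelet, inhibitor and inducer items set none either. A control treated for a suspicion later refuted would stay in. So would one started on prophylaxis after the Day 29 visit but before imaging, which SAP 8.3 accepts up to Day 40. Those gaps are real, but the protocol allows such use, so it is not a deviation.

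**Conclusion.** The concern holds. The list omits the prohibited treatment that most directly meets the Protocol 8.2 test, and SAP 6.3 makes that list decisive. A correctly assigned control child anticoagulated before any event stays in the Evaluable population and is not counted toward the trigger, unless the child meets another listed criterion. This should be corrected, but it affects one conditional sensitivity analysis only.

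The size rests on assumed contamination rates, no contamination in the apixaban arm, and the planning rates of 17% and 8.5%. When treatment is unrelated to risk and halves it, the RR moves from 0.50 to 0.505 at 2% contamination and 0.556 at 20%. When higher-risk controls are treated, removal can help, make no difference or do harm, depending on whether k(1 − e) is below, equal to or above 1. The omission itself is certain from the text; how much it matters in practice is not known.

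**What to change.** Add Protocol 3.4.1 item 1 to the criteria in SAP 7.2.1, for both arms, with these limits:

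- Systemic use only; CVAD heparin flushes and local tPA stay exempt.
- Started during the Intended Treatment Period, which "will refer to the period from day of randomization through Day 29 visit". Later use must not count, because Protocol 3.2 provides for it: "If the investigator considers that the subject should receive continuous VTE prevention after the Day 29 visit", standard of care is to be arranged.
- Started before any suspected or adjudicated VTE, so that treatment of an event does not remove the event.

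Report the number of such children by arm, split into use before and after a suspected VTE, whether or not the 10% trigger is met.

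The SAP should also state the drawback. The exclusion depends on treatment after randomization and need not recover the uncontaminated RR. An asymptomatic DVT found at Day 29 in a child already on LMWH would be removed with the child, because its onset is unknown. The Evaluable result should be read beside the ITT result.

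The cost is one SAP line and one count by arm. Concomitant medications are already collected and summarised by class and arm. The added work is to date each anticoagulant start against any suspected event and to separate systemic use from line care.

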7.2.2 Coronavirus (Covid-19)

Focused summaries, as well as listings will be provided for the number and percent of participants affected by Covid-19 for the following areas:

Disposition: The number and percent of participants who were not randomized, prematurely discontinued study drug, or prematurely withdrew from the study (See Section 7.3.1) will also be summarized by the combination of primary reason for not being randomized, prematurely discontinued study drug, or prematurely withdrawn from the study and whether these reasons were Covid-19 related. Covid-19 related status events will also be listed.

Study Visits: Study visits not performed, or performed using an alternate method than specified in the protocol will be listed.

Imaging Not Performed: Reasons for not obtaining an image will be summarized, including whether the reason involved Covid-19. Missing data will be handled in the manner specified in [Section 7.5](#).

Adverse Events: Covid-19 event will be treated as an event of interest. The number and percent of participants with a Covid-19 event will be summarized by SOC and preferred term (See [Section 7.6](#)), as well as listed.

Additional subset analyses may be performed excluding participant data affected by Covid-19, if the effect exceeds 10% of the study population.

7.3 Study Population

7.3.1 Subject Disposition

The number of subjects enrolled into the study, and the number of subjects enrolled but not randomized together with the reasons for not being randomized will be summarized. The reasons for not being randomized will be taken from the CRF pre-randomization status page.

The summaries described below will also be presented by age stratum when applicable.

The number of randomized subjects and the number of subjects discontinuing during each study period together with the reasons for discontinuation will be summarized by treatment group. The reasons for discontinuation will be taken from the end-of-treatment and the end-of-follow-up status pages of the CRF.

The frequency of subjects randomized in each country and in each region will be tabulated by randomized treatment group and for all randomized subjects combined.

7.3.2 Demography and Baseline Characteristics

The following demographic and baseline characteristics will be summarized by randomized treatment group and for all subjects combined. Continuous variables will be summarized using mean and standard deviation. Categorical variables will be summarized using counts and percentages.

- Geographic region
- Country
- Age
- Age group (<10, 10≤18 years old)
- Gender

- Race
- Ethnicity
- Weight
- Weight group (<35, ≥35 kg)
- Height
- Platelet count
- Vital signs (systolic blood pressure, diastolic blood pressure, and heart rate)
- Level of renal impairment (severe, moderate, mild, normal)

The summaries will be presented for the randomized/ITT population. All summaries will be further tabulated by age stratum.

In addition, medical history will be summarized for the randomized/ITT population.

Any imbalances between the treatment groups will be assessed in reviewing the summaries and any differences deemed clinically relevant to the efficacy or safety comparisons may be investigated by controlling for the characteristic in a supplemental analysis.

7.4 Extent of Exposure

7.4.1 Study Therapy

Extent of exposure to the study drug is defined as the number of days from first treatment to last treatment (date of last treatment - date of first treatment + 1). Summary of exposure to study drug will show the distribution of the number of days on drug together with the mean days of exposure, for the apixaban treatment group. Additionally, the extent of exposure will be summarized excluding any interruptions.

Treatment compliance (TC) will also be summarized for apixaban treatment group.

For each subject in the apixaban treatment group, treatment compliance (TC) with apixaban is defined as follows.

$$TC = \frac{\text{number of doses taken (tablets or oral solution)}}{(\text{last dose date} - \text{first dose date} + 1 - I) \times 2^{-k+R}} \times 100\%, \text{ where}$$

k=0, if two doses are given on the first day of apixaban

k=1, if one dose is given on the first day of apixaban

R: number of doses needed to be retaken because of the regurgitation, and

I: total number of days study drug was interrupted with a **protocol-defined** interruption.

Regarding protocol-defined interruptions, the number of days from first to last dose of apixaban will exclude the days that subjects have protocol defined dose interruption such as planned lumbar puncture, for conservative side, 2 days will be excluded for one planned lumbar puncture, and 3 days will be excluded for one traumatic lumbar puncture.

Extent of exposure to the study drug will be further tabulated by age stratum.

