For a subject who experiences a reaction to asparaginase during the infusion and has to switch to Erwinia asparaginase during the induction chemotherapy, it is recommended that the subject continue the study treatment. The percentage of the original asparaginase dose delivered will be collected in the patient chart and case report form.

A platelet count $\geq 20,000$ / μ L must be obtained within 24 hours prior to the first dose of apixaban. A subject may be transfused platelets per investigator's clinical judgment but may not be transfused solely to meet entry criteria.

Apixaban should be discontinued at least 24 hours prior to any planned lumbar puncture (LP) and resumed no sooner than 18-24 hours after the procedure. In the event of a traumatic lumbar puncture (defined in this protocol as a lumbar puncture with ≥ 10 red blood cells (RBCs)/ μ L of cerebrospinal fluid (CSF), apixaban should be held for 48 hours after the procedure.

For example, for a LP scheduled on the morning of Day 8, the Day 7 PM and Day 8 AM and PM doses of apixaban should be held and may be restarted the morning of Day 9. If a subject will receive an LP on Day 29, the last dose will be the AM dose on Day 28.

During the study treatment period, study visits will occur on Day 8 \pm 5 days, Day 15 \pm 5 days, Day 22 \pm 5 days and Day 29 \pm 5 days of planned 3-4 drug systemic induction chemotherapy. Windows for study visits after randomization will be \pm 5 days. The timing of these study visits will coincide with standard of care visits for pediatric subjects in induction chemotherapy. Visits will consist of reporting adverse events (including bleeding and secondary endpoints as described below), monitoring medication adherence and laboratory testing. On the Day 29 visit, imaging evaluation will occur for all randomized subjects except for those who are discontinued from protocol therapy. For those subjects randomized to apixaban, imaging evaluations will be performed within 3 days but no more than 5 days of discontinuing apixaban. For those subjects randomized to the standard of care arm, it would be preferred that the imaging evaluations be performed within three days but no more than 5 days from Day 29 (Day 24 to Day 34). The evaluation will include a) a bilateral Doppler ultrasound that will include imaging of the venous system in which the CVAD is placed and the similar location for the opposite side; and b) an echocardiogram to assess for right atrial

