Lumbar punctures (LPs)	
Apixaban should be discontinued at least 24 hours prior to any planned lumbar puncture (LP) ie, there should be at least 24 hours between the last dose of apixaban and the planned LP. Apixaban should be resumed no sooner than 18 - 24 hours after the procedure. In the event of a traumatic lumbar puncture (defined in this protocol as a lumbar puncture with ≥ 10 red blood cells (RBCs)/μL of cerebrospinal fluid (CSF)⁶⁰, apixaban should be held for 48 hours after the procedure.
 
For example: for a LP scheduled on the morning of Day 8 :
 
 1. Discontinue apixaban for at least 24 hours prior to the Day 8 Lumbar Puncture (hold apixaban the night before and the morning of the procedure, the Day 7 PM and Day 8 AM and PM doses of apixaban). 2. Resume apixaban 18-24 hours after the Day 8 AM Lumbar Puncture (resume apixaban with the AM dose on the day after the procedure, Day 9). 
Recommend participating institutions follow local standards of care regarding minimum platelet thresholds prior to lumbar punctures.
 
In the event of a traumatic lumbar puncture (defined in this protocol as a lumbar puncture with ≥ 10 red blood cells (RBCs)/μL of cerebrospinal fluid (CSF), apixaban should be held for 48 hours after the procedure.
 
The last dose of apixaban will be on Day 29\pm5 of induction chemotherapy.
 
Lumbar punctures for study subjects should only be performed by trained personnel.

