4.7 Treatment Compliance

Each time study medication is dispensed, compliance will be reinforced.

For inpatients, apixaban will be administered in the clinical facility under the supervision of clinical staff. The date, time and volume or dosage of administered drug will be recorded at the clinical site by clinical personnel in the patient's diary and eCRF. If an infant or a young child regurgitates a portion of or the entire drug product during or after administration, this should be recorded in the eCRF.

At each study visit, the patient/parents should bring the study medication and compliance will be assessed based upon subject's/parents interview and a count of the tablets or volume of solution returned. Compliance should be between $\geq 80\%$ and $\leq 120\%$ of that prescribed, excluding the protocol defined dose interruption period. The investigator (or designee) will record the amounts of study medication dispensed and returned at each visit, as well as document reasons for non-compliance in the source document. The dates of all study medication dosing, including interruptions, missed doses or overdose, must be recorded on the eCRF. If a subject is not $\geq 80\%$ compliant after exclusion of the protocol defined dose interruption period, then the period of noncompliance should be noted as a protocol deviation and the sponsor should be notified. The subject should be re-educated regarding recording these values.

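### The compliance formula turns the lumbar-puncture hold into whole days and so, in the protocol's own example, removes one dose too many per puncture and overstates compliance by about 2 points each

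*SAP*

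**What the plan says.** SAP 7.4.1 defines TC as doses taken divided by an expected number of doses. The expected number is the days from first to last dose, less I (days of protocol-defined interruption), times 2, minus k, plus R (doses retaken after regurgitation). The term k corrects the first day: "k=1, if one dose is given on the first day of apixaban". There is no matching term for the last day. For I, the SAP fixes the allowance per LP: "for conservative side, 2 days will be excluded for one planned lumbar puncture, and 3 days will be excluded for one traumatic lumbar puncture".

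The protocol describes the hold in doses. Its Synopsis (Study Design) works through a Day 8 LP done in the morning: "the Day 7 PM and Day 8 AM and PM doses of apixaban should be held and may be restarted the morning of Day 9". Table 4.5.2-1 in Protocol 4.5.2 gives the same case: "hold apixaban the night before and the morning of the procedure, the Day 7 PM and Day 8 AM and PM doses of apixaban". The rule behind it is at least 24 hours off drug before the LP, resumption no sooner than 18-24 hours after it, and 48 hours after a traumatic LP.

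Protocol 4.7 sets a compliance range of 80% to 120%, "excluding the protocol defined dose interruption period".

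**The concern.** The SAP and the protocol measure the same hold in different units. An interruption of two elapsed days on a twice-daily schedule does not skip four doses, because doses are taken at both ends of the gap. If I is counted in elapsed days and then multiplied by 2, the expected number of doses is too low and TC is too high. The SAP describes this choice as being on the conservative side, yet for an adherence measure with a lower limit an error upward is not conservative. At stake is the accuracy of the only adherence figure reported for the only arm that is dosed, which readers will want if the efficacy result is null or diluted.

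**Working it through.** **Inputs.** Days removed per LP: 2 planned, 3 traumatic (SAP 7.4.1). Doses held in the morning-LP example: 3 (Protocol Synopsis and Table 4.5.2-1). Hold after a traumatic LP: 48 hours (Table 4.5.2-1). More than 3 scheduled LPs between randomization and the Day 29 visit is an exclusion (Protocol 3.3.2). Assumed for illustration: 28 dosing days, k = 0, R = 0, two doses on the last day, every dose not held is taken. The formula's printed exponent is read as a text-extraction artefact for × 2 − k + R.

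**Where 2 and 3 days come from.** They reproduce as elapsed time off drug: 24 + 24 = 48 hours = 2 days (Day 7 AM to Day 9 AM), and 24 + 48 = 72 hours = 3 days.

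**As doses.** A gap of G hours on a 12-hour schedule omits G/12 − 1 doses:
- 48/12 − 1 = 3, which matches the protocol example.
- 72/12 − 1 = 5 (Day 7 PM to Day 9 PM, restart Day 10 AM). The protocol does not print this count.

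The SAP removes 2 × 2 = 4 and 3 × 2 = 6, one more in each case.

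**Effect on TC under perfect dosing.** With L planned LPs, doses due are 56 − 3L and the SAP denominator is (28 − 2L) × 2.

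| Planned LPs | Doses due and taken | SAP denominator | TC |
|---|---|---|---|
| 1 | 53 | 52 | 101.9% |
| 2 | 50 | 48 | 104.2% |
| 3 | 47 | 44 | 106.8% |

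With traumatic LPs, (56 − 5L)/[(28 − 3L) × 2] gives 51/50 = 102.0% for one and 41/38 = 107.9% for three.

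**Effect on a child who misses doses.**
- 1 planned LP, 42 doses taken: 42/53 = 79.2% of doses due; the SAP gives 42/52 = 80.8%.
- 2 planned LPs, 39 doses taken: 39/50 = 78.0%; the SAP gives 39/48 = 81.3%.
- 3 planned LPs, 36 doses taken: 36/47 = 76.6%; the SAP gives 36/44 = 81.8%.

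**Last day.** The Synopsis says that with a Day 29 LP the last dose is Day 28 AM, so one dose is due that day. With LPs on Days 8 and 29 (the days in the Appendix 12 outline), doses due are 56 − 3 − 1 = 52. If only the Day 8 LP counts in I, the SAP denominator is (28 − 2) × 2 = 52 and TC = 100%: the missing last-day correction cancels the excess. If the Day 29 LP were also counted, TC would be 52/48 = 108.3%. The SAP describes I within the span from first to last dose, but does not say explicitly how a Day 29 LP is treated.

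**Clock time.** With assumed dosing at 08:00 and 20:00:
- LP at 08:00: 3 doses held (5 if traumatic).
- LP at 07:00: 4 (6), because the Day 7 08:00 dose is only 23 hours before.
- LP at 14:00: 3 if dosing resumes from 18 hours, 4 if from 24 hours (6 if traumatic).

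For a child who holds 4 doses, the SAP gives 52/52 = 100%.

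**The case against.** The strongest reply is that three doses is one example and not the rule. The hold times are minimums, so four doses (six if traumatic) can be fully compliant, and the SAP allowance is then exact. This stands. A reader might infer that compliance is inflated for every child; the documents do not support that. It also means that hard-coding 3 and 5 would understate compliance in children who held more.

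Second, the figures above 100% assume two doses on the last day and every LP before the last dose. With a Day 29 LP the excess from one earlier LP disappears, and with three LPs of which one is on Day 29, perfect dosing reads 49/48 = 102.1% and not 106.8%. This stands too, though the cancellation comes from a second omission and not from design.

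Third, a reader might infer that children below the 80% limit escape being recorded as deviations. The documents do not support that. Under Protocol 4.7 compliance is assessed at visits from interviews and from counts of returned drug, and the SAP applies no 80% cut-off to TC. Nor does TC decide who is in the Evaluable population: SAP 7.2.1 uses more than 3 consecutive undosed days, excluding protocol-defined interruptions.

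Last, the word conservative may refer to a generous hold window and not to the direction of TC; Protocol 4.5.2 uses the word of interruptions themselves. That is possible, but in a definition of compliance the phrase will be read as describing the estimate, and there it misleads.

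**Conclusion.** The point holds in a limited form. The SAP counts the LP interruption in elapsed days where the formula needs doses. In the only case the protocol works through, the denominator is one dose too small per on-treatment LP, and TC rises by about 2 points per LP, to 106.8% with three planned LPs under the stated 28-day assumptions. Removing too many doses can only raise TC. The size depends on LP clock time, on when dosing resumes and on the number of doses on the last day, and it is zero for some children. The figure of 5 for a traumatic LP is a derivation.

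The consequence is small: a descriptive adherence summary for the apixaban arm is misstated for some children. No analysis population, efficacy result or site deviation report depends on it. The change is worth making because it costs little, not because a trial conclusion is at risk.

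**What to change.** In SAP 7.4.1, count the protocol-defined interruption in doses:

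TC = doses taken / [(last dose date − first dose date + 1) × 2 − H − k − m + R] × 100%

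- H is the number of scheduled doses between first and last dose that were actually held under the LP rule, taken from the eCRF and diary. It replaces the fixed 2 or 3 days and should not be hard-coded as 3 or 5.
- m = 1 if only one dose is due on the last day, otherwise 0, to match k.
- State that a Day 29 LP after the last dose contributes nothing to H (or to I, if I is kept).
- Delete the phrase about the conservative side.

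Check: one planned LP gives 53/(56 − 3) = 100%; LPs on Days 8 and 29 give 52/(56 − 3 − 1) = 100%; a child who holds 4 doses gives 52/(56 − 4) = 100%.

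The cost is SAP wording and a derivation that matches held doses to LP dates. No new collection of dosing data is needed: Protocol 4.7 already requires the dates of all dosing, interruptions and missed doses on the eCRF, and Protocol 5.2 makes a diary with dose dates and times mandatory. The change affects only the calculation and takes no position on the clinical hold rule.
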